5.3 Exclusion Criteria

Subjects who meet **any** of the following exclusion criteria will not be eligible for the study:

1. Prior treatment for CHB; specifically
 - a. lamivudine, telbivudine or adefovir (any duration)
 - b. NrtI treatment for >4 weeks
 - c. HBV core inhibitors (any duration)
 - d. Previous treatment with an investigational agent for HBV infection
2. Co-infection with human immunodeficiency virus (HIV), hepatitis C virus (HCV), hepatitis E virus (HEV), or hepatitis D virus (HDV)
3. Females who are lactating, or wish to become pregnant during the course of the study
4. History or evidence of advanced liver disease or hepatic decompensation (including jaundice, ascites, portal hypertension, gastrointestinal bleeding, esophageal varices, hepatic encephalopathy) at any time prior to, or at the time of Screening
5. History of persistent alcohol abuse (alcohol consumption exceeding 2 standard drinks per day on average [1 standard drink = 10 grams of alcohol]) or illicit drug abuse within 3 years of Screening
6. Clinically significant cardiac or pulmonary disease, chronic or recurrent renal or urinary tract disease, liver disease other than CHB, endocrine disorder, autoimmune disorder, diabetes mellitus requiring treatment with insulin or hypoglycemic agents, neuromuscular, musculoskeletal, or mucocutaneous conditions requiring frequent treatment, seizure disorders requiring treatment, ongoing infection or other medical conditions requiring frequent medical management or pharmacologic or surgical treatment that in the opinion of the Investigator or the Sponsor makes the subject unsuitable for study participation
7. History of HCC

8. History of malignancy other than HCC unless the subject's malignancy has been in complete remission off chemotherapy and without additional medical or surgical interventions during the 3 years before Screening
9. Poorly controlled or unstable hypertension; or sustained systolic blood pressure (BP) ≥ 160 mmHg or < 90 mmHg, or diastolic BP > 95 mmHg or < 50 mmHg at Screening
10. History or presence of electrocardiogram (ECG) abnormalities deemed clinically significant including:
 - a. Personal or family history of prolonged QT syndrome or family history of sudden death
 - b. QTcF > 450 msec (males) or > 470 msec (females) or < 300 msec at Screening or Day 1 visit
 - c. ECG with QRS and/or T-wave judged to be unfavorable for a consistently accurate QT measurement as judged by the Investigator at Screening

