 - PK Samples: Predose samples for ABI-H2158 or PBO and ETV. Postdose samples for ABI-H2158 and ETV between 2 to and 4 hours following study drug administration. See [Section 7.8.8](#) for additional information.

- Study drug dispensation
- Study drug administration (ABI-H2158 or PBO and ETV) during clinic visit. Provide dosing diary to the subject and record first dose administration

7.4 Study Weeks 2 Through 72

The following assessments are performed at Study Weeks 2, 4, 8, 12, 16, 20, 24 and then every 4 weeks thereafter through Week 72 (inclusive) unless otherwise indicated. A visit window of ± 3 days is applied to each visit through Week 24 and ± 5 days from Weeks 28 through 72:

- Measure body weight (Weeks 24, 48, and 72 only)
- Vital signs (temperature, heart rate, respiration rate and blood pressure)
- Complete physical examination (excluding breast and genitalia, unless indicated; Weeks 24, 48 and 72 only)
- Symptom-directed physical examination (Not at Weeks 24, 48 or 72)
- 12-lead ECG (Weeks 12, 24, 36, 48, 60 and 72 only)
- Review concomitant medications
- Review AEs
- Review dosing diary
- Assess drug accountability (not at Week 2)
- Study drug dispensation (not at Week 2; through Week 68 only for ABI-H2158 or PBO; and through Week 72 for ETV)
- Study drug administration (ABI-H2158 or PBO and ETV) during clinic visit (Weeks 2, 4, 8, 12, 24, 28, 48 and 72 only)
- Laboratory analyses (additional details are provided in the Laboratory Manual):
 - Safety Labs: Chemistry, hematology, coagulation (not at Week 2), urinalysis (not at week 2), and urine pregnancy test (if positive on dipstick, serum pregnancy test should be performed).
 - Virology/Immunology: HBV DNA, HBV pgRNA, HBsAg (not at Week 2), HBeAg (not at Week 2), HBcrAg (not at Week 2), HBsAb and HBeAb (Weeks 12, 24, 36, 48, 60, and 72 only), sample for HBV sequencing and HBV nucleic acids
 - PK Samples: Predose samples for ABI-H2158 or PBO and ETV on Weeks 4, 48, and 72 only. Samples for ABI-H2158 or PBO and ETV 30 min to 2 hours postdose on Weeks 2, 8, 12, 24, and 28. Samples for ABI-H2158 or PBO and ETV 4 to 6 hours postdose on Weeks 16 and 20 only). See [Section 7.8.8, Table 6](#) for additional information.

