10.4.4 Analysis of Safety Endpoints

The safety parameters to be assessed are described in [Section 7.8](#) Displays for safety results will utilize descriptive statistics. No formal hypothesis testing of safety data is planned.

Adverse events will be coded using the Medical Dictionary for Regulatory Activities (MedDRA). Incidence of each body system and preferred term will be tabulated for each treatment group. Treatment-emergent adverse events (TEAE) are defined as those reported on or after the first dose of study drug through 28 days from the last dose of study drug. Summaries will include all TEAEs, TEAEs

considered related to study treatment by investigators, Graded TEAEs, and SAEs. All AEs, emergent or non-emergent, will be listed by subject. Any TEAEs leading to premature discontinuation from the study intervention and serious TEAEs will be presented by listing.

Clinical laboratory results will be summarized descriptively by treatment group including values, changes from Baseline, and incidence of laboratory abnormalities. Laboratory results will be listed for each subject.

Vital sign data and ECG findings reported at each visit will be displayed by treatment, using descriptive statistics for observed and change from Baseline values.

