Prolonged PR Interval or AV Block	PR interval 0.21 to < 0.25 seconds	PR interval \geq 0.25 seconds OR Type I 2nd degree AV block	Type II 2nd degree AV block OR Ventricular pause \geq 3.0 seconds	Complete AV block
Prolonged QTc Interval¹	0.45 to 0.47 seconds	> 0.47 to 0.50 seconds	> 0.50 seconds OR  0.06 seconds above baseline	Life-threatening consequences (eg, Torsade de pointes, other associated serious ventricular dysrhythmia)
Thrombosis or Embolism Report only one	NA	Symptoms AND No intervention indicated	Symptoms AND Intervention indicated	Life-threatening embolic event (eg, pulmonary embolism, thrombus)

¹ As per Bazett's formula.

Dermatologic				
Parameter	Grade 1 Mild	Grade 2 Moderate	Grade 3 Severe	Grade 4 Potentially Life-Threatening
Alopecia (scalp only)	Detectable by study subject, caregiver, or physician AND Causing no or minimal interference with usual social & functional activities	Obvious on visual inspection AND Causing greater than minimal interference with usual social & functional activities	NA	NA
Bruising	Localized to one area	Localized to more than one area	Generalized	NA
Cellulitis	NA	Non-parenteral treatment indicated (eg, oral antibiotics, antifungals, antivirals)	IV treatment indicated (eg, IV antibiotics, antifungals, antivirals)	Life-threatening consequences (eg, sepsis, tissue necrosis)
Hyperpigmentation	Slight or localized causing no or minimal interference with usual social & functional activities	Marked or generalized causing greater than minimal interference with usual social & functional activities	NA	NA
Hypopigmentation	Slight or localized causing no or minimal interference with usual social & functional activities	Marked or generalized causing greater than minimal interference with usual social & functional activities	NA	NA
Petechiae	Localized to one area	Localized to more than one area	Generalized	NA
Pruritus ³ (without skin lesions)	Itching causing no or minimal interference with usual social & functional activities	Itching causing greater than minimal interference with usual social & functional activities	Itching causing inability to perform usual social & functional activities	NA

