7.5. Electrocardiogram Results

A shift table of the Investigators' assessment of ECG results at each visit compared with baseline values will be presented by treatment group using the following categories:

- normal

- abnormal (not clinically significant)
- abnormal (clinically significant)
- missing/not done

The number and percentage of subjects in each cross-classification group of the shift table will be presented. Subjects with a missing value at Baseline or postbaseline will not be included in the denominator for percentage calculation.

A by-subject listing for ECG assessment results will be provided by subject ID number and visit in chronological order.

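### Entry uses QTcF but AE grading uses Bazett, on-treatment ECGs have no time relative to dose, and SAP 7.5 omits the numerical ECG summary promised in protocol 10.4.4

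*Combined protocol and SAP*

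**What the plan says.** **Correction formula.** Protocol Section 5.3, criterion 10b, excludes subjects with "QTcF > 450 msec (males) or > 470 msec (females) or < 300 msec at Screening or Day 1 visit". Appendix 2, which Section 8.2 makes the severity scale for AEs, sets Grade 1 prolonged QTc at "0.45 to 0.47 seconds" and Grade 2 at "> 0.47 to 0.50 seconds". Grade 3 is above 0.50 seconds, or a rise expressed as "0.06 seconds above baseline" (the comparison sign is lost in our copy). The footnote to that row reads "As per Bazett's formula". Section 7.8.4 names no formula for on-treatment ECGs and leaves their conduct to local practice and equipment.

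**Timing.** The Day 1 ECG is taken before dosing (Section 7.3). Section 7.4 lists the on-treatment ECGs by week only: "12-lead ECG (Weeks 12, 24, 36, 48, 60 and 72 only". Section 7.8.4 asks for 10 minutes of supine rest but gives no time relative to dose.

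**Analysis.** Protocol 10.4.4 states: "Vital sign data and ECG findings reported at each visit will be displayed by treatment, using descriptive statistics for observed and change from Baseline values". SAP 7.5 plans instead "A shift table of the Investigators' assessment of ECG results at each visit compared with baseline values", with the categories normal, abnormal not clinically significant, abnormal clinically significant, and missing, plus a listing. SAP 7.3 keeps the observed and change-from-Baseline display for vital signs.

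**The concern.** The two formulas differ systematically with heart rate, so the same tracing can sit in one band for eligibility and another for severity. AEs are part of a primary endpoint, and a grade that moves with heart rate is harder to interpret. Untimed ECGs leave unknown how much drug was present at each tracing, while the baseline is a drug-free predose value. The SAP then reports no QTc value at all. If mean QTc moved in the ABI-H2158 arm while each subject stayed within the investigator's normal category, no planned table would show it.

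**Working it through.** The documents contain no QT calculation to reproduce, and the sample size has no statistical basis, so power does not enter.

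**1. Size of the formula mismatch.** By definition QTcB = QT/RR^(1/2) and QTcF = QT/RR^(1/3), with RR = 60/HR seconds. Hence QTcB = QTcF × (HR/60)^(1/6). The documents give no heart rates, so those below are assumptions. The QTcF values of 450 and 470 ms are the male and female limits of criterion 10b.

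| HR (bpm) | Ratio | QTcF 450 ms | QTcF 470 ms |
|---|---|---|---|
| 50 | 0.970 | 437 (ungraded) | 456 (Grade 1) |
| 60 | 1.000 | 450 (Grade 1) | 470 (Grade 1) |
| 75 | 1.038 | 467 (Grade 1) | 488 (Grade 2) |
| 90 | 1.070 | 481 (Grade 2) | 503 (Grade 3) |

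These grades show where the value falls in the Appendix 2 bands. They apply in practice only if the finding is recorded as an AE.

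Subjects further from the limit are less affected. The rate needed to reach a threshold t is HR = 60 × (t/QTcF)^6. For t = 450 ms this gives about 79 bpm from QTcF 430 and about 122 bpm from QTcF 400.

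For the 60 ms change limb of Grade 3, with Bazett used throughout and QTcF constant, the rate would have to go from 60 to about 127 bpm (QTcF 450) or 134 bpm (QTcF 420). Resting heart rate alone does not plausibly do that. Mixing formulas matters more: a Baseline held as QTcF 430 and a later Bazett value at 90 bpm give 430 × 1.070 = 460 ms, an apparent rise of 30 ms, which is half the 60 ms threshold.

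**2. Exposure at an untimed ECG.** Protocol Table 2, 300 mg once daily, Day 10: Cmax 4.21 µg/mL, C24hr 1.38 µg/mL, median Tmax 2 h (range 2 to 4). C24hr/Cmax = 1.38/4.21 = 0.33. If a QT effect were linear in concentration (an assumption), 10 ms at peak would be 10 × 0.33 = 3.3 ms at trough.

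The six ECG visits divide as follows under Section 7.4 and Appendix 1:
- Weeks 12 and 24: in-clinic dose and a PK sample 30 min to 2 h postdose.
- Weeks 48 and 72: in-clinic dose, predose PK sample only.
- Weeks 36 and 60: no in-clinic dose. Section 4.3 says ABI-H2158 or placebo is given in the clinic on study visit days, so these passages need reconciling.

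**3. Protocol against SAP.** Protocol 10.4.4 treats vital signs and ECG findings in one sentence and promises the same statistics for both. SAP 7.3 delivers them for vital signs; SAP 7.5 does not for ECG. SAP 6.2 records changes from the protocol for efficacy analyses only, and SAP 7.5 gives no reason for the reduced ECG output.

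**The case against.** A reader might infer that QT grades are inflated by heart rate, that a real drug effect will be missed because ECGs are taken at trough, and that the comparison between arms is biased. The documents do not support any of these.

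- **Inflation.** Bazett lowers QTc below 60 bpm. A man at QTcF 450 ms and 75 bpm is Grade 1 under either formula. Part of the female discrepancy comes from grade bands that are not sex-specific, and a single formula would leave that in place.
- **Route to the endpoint.** Under Section 7.8.4 an ECG abnormality becomes an AE only if it is confirmed and judged clinically significant, or leads to discontinuation or treatment. An eligible subject's Day 1 tracing does not by itself carry a grade.
- **Between-arm bias.** The same scale applies to both arms, and the documents give no evidence that ABI-H2158 changes heart rate.
- **Missed at trough.** The ECGs are untimed, not set at trough, and those at Weeks 12 and 24 may well be postdose. The 0.33 ratio comes from six healthy subjects with CVs of 92% (Cmax) and 126% (C24hr).
- **No signal.** The 9-month monkey study found no ECG effect at a mean Cmax averaging 17.1 µg/mL, against 8.4 µg/mL in CHB patients at 300 mg (17.1/8.4 = 2.0). QT characterisation is not a study objective.
- **Termination.** The SAP was written after development stopped on 01 September 2021 and limits itself to key safety and efficacy endpoints. Visits already made cannot be re-timed.

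All of this stands, and it limits the point to consistency and reporting. It does not reconcile the two formulas. Termination explains a shorter SAP in general, but not why the display was kept for vital signs and dropped for ECG while safety remains a primary objective in SAP 1.1.

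**Conclusion.** The point holds as a matter of measurement consistency and reporting. The formula mismatch is real but minor: at the male entry limit it amounts to about +31 ms at 90 bpm and −13 ms at 50 bpm, at assumed heart rates, and much of the population will be further from a grade boundary. The missing ECG timing leaves exposure at each tracing undefined, between about one third of peak and peak on the healthy-subject figures; it does not show that an effect would be missed. The most consequential part is the SAP gap, because it can still be addressed in the final analysis. Whether it can be closed depends on whether QT interval data were captured. Section 7.8.4 describes interpretation of tracings on local equipment, Section 7.8 says some evaluations may not be on the case report form, and we do not have the form. None of this touches the primary efficacy analysis.

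**What to change.** 1. **Formula.** Reconcile criterion 10b and the Appendix 2 footnote to a single correction formula. QTcF is the one already used at Screening and Day 1. This is a wording change and removes the heart-rate gap between entry and grading; it does not change the non-sex-specific bands.
2. **Timing.** Record dose and ECG clock times at every ECG visit. Take the Week 12 and Week 24 ECGs after the in-clinic dose, together with that visit's postdose PK sample. The PK window closes at the Day 10 median Tmax, so such an ECG would be near peak for some subjects and before it for others; the recorded times let the analyst see which. For this terminated trial, the change applies only to any future use of the protocol. Its cost is an ECG later in a stay that subjects already make at two visits.
3. **SAP 7.5.** Where interval data were collected, add QTcF observed and change from Baseline by arm and visit, with counts at the Appendix 2 cut-offs (450, 470 and 500 ms, and 60 ms above Baseline). If the data are not available or the display is deliberately dropped, state the departure from protocol 10.4.4 and why. The cost is one more table.

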HBV	hepatitis B virus
HLGT	high-level group term
HLT	high-level term
ID	identification
IPD	important protocol deviation(s)
IRT	interactive response technology
LLOQ	lower limit of quantitation
LLT	lower-level term
LOQ	limit of quantitation
MedDRA	medical dictionary for regulatory activities
PBO	placebo

PD	protocol deviation(s)
pgRNA	pregenomic RNA
PT	preferred term
PK	pharmacokinetics
Q1, Q3	first quartile, third quartile
QD	once daily
SAE	serious adverse event
SAP	statistical analysis plan
SD	standard deviation
SE	standard error
SOC	system organ class
TEAE	treatment-emergent adverse event
TFLs	tables, figures, and listings
ULN	upper limit of normal

1. INTRODUCTION

Study ABI-H2158-201 is a Phase 2a, multicenter, randomized, single-blind, placebo (PBO)-controlled, multiple cohort study evaluating ABI-H2158-containing regimens in chronic hepatitis B virus (HBV) infection (cHBV). The target population is male or female subjects with cHBV, 18 to 65 years of age, inclusive, with no evidence of cirrhosis or end-stage liver disease. Cohort 1 will enroll treatment-naïve subjects with hepatitis B virus “e” antigen (HBeAg) positive cHBV. Cohort 2 will enroll treatment-naïve subjects with HBeAg negative cHBV.

This statistical analysis plan (SAP) describes the statistical analysis methods and data presentations to be used in tables, figures, and listings (TFLs) in the clinical study report (CSR) for Study ABI-H2158-201. This SAP is based on the Study Protocol Amendment 2, dated 14 December 2020; UK country-specific protocol amendment, dated 17 December 2020; Korea-country specific protocol amendment, dated 05 February 2021; ABI-H2158-201 Protocol Clarification Letter for Amendment 2; dated 14 Dec 2020, 07 September 2021; and the electronic case report form (eCRF). On 01 September 2021, Assembly made the decision to discontinue the development of ABI-H2158 following the observation of elevated alanine aminotransferase (ALT) levels consistent with drug-induced liver injury (DILI) in study ABI-H2158-201. Therefore, only key safety and efficacy endpoints will be performed. The SAP will be finalized before final database lock. Any changes made after the finalization of the SAP will be documented in the Synoptic CSR.

1.1. Study Objectives

The primary objectives of this study are as follows:

- To evaluate the safety and tolerability of ABI-H2158 when administered in combination with entecavir (ETV) in subjects with cHBV
- To evaluate the effect of ABI-H2158 in reducing HBV DNA in subjects with cHBV

The secondary objectives of this study are as follows:

- To evaluate the pharmacokinetics (PK) of ABI-H2158 and ETV in subjects with cHBV
- To evaluate the effect of ABI-H2158 in reducing HBV pregenomic RNA (pgRNA) levels in subjects with cHBV
- To evaluate the effect of ABI-H2158 in reducing HBV antigens (ie, HBeAg, hepatitis B core-related antigen [HBcrAg] and hepatitis B surface antigen [HBsAg]) in subjects with cHBV
- To evaluate the effect of ABI-H2158 on normalization of ALT in subjects with abnormal ALT
- To evaluate the emergence of resistance to ABI-H2158 when administered in combination with ETV

The exploratory objectives of this study are as follows:

- To assess the relationship between new and known viral biomarkers and virologic and/or clinical outcomes
- For subjects who provide an optional pharmacogenomic sample, to evaluate the potential contribution of host genomics to clinical or virologic outcomes and/or drug disposition

1.2. Study Design

This study will assess the safety, antiviral activity, and pharmacokinetics (PK) of ABI-H2158 administered once daily (QD) in combination with ETV in subjects with cHBV. Multiple parallel cohorts will be enrolled in the study.

In Cohort 1, approximately 40 treatment-naïve subjects with HBeAg positive cHBV will be randomized in a 3:1 ratio to receive 300 mg ABI-H2158+ETV (n=30) or matching PBO+ETV (n=10) for 72 weeks (Figure 1-1). In Cohort 2, approximately 40 treatment-naïve subjects with HBeAg negative cHBV will be randomized in a 3:1 ratio to receive 300 mg ABI-H2158+ETV (n=30) or matching PBO+ETV (n=10) for 72 weeks (Figure 1-1). Treatment assignments for Cohort 1 will be stratified by the HBV DNA level measured at the Screening visit (ie, $\geq 8.0 \log_{10}$ IU/mL versus $< 8.0 \log_{10}$ IU/mL) and for Cohort 2 will be stratified by the HBV DNA level measured at the Screening visit (ie, $\geq 6.0 \log_{10}$ IU/mL versus $< 6.0 \log_{10}$ IU/mL).

After completing treatment at Week 72, or following premature treatment discontinuation, all subjects will enter a 24 week follow-up period. During the follow-up period all subjects will remain on ETV and undergo the follow-up assessments. After completing the 24-week follow-up period, all subjects will resume management by their treating physician in accordance with local standard of care.

[figure not shown]
The schedule of assessments is presented in Protocol Appendix 1.

An assessment of PK data will also be performed after all subjects have completed study Week 4 (or discontinued study without completing Week 4) in order to confirm the absence of important drug interactions between ABI-H2158 and ETV at steady state.

Following the early termination of Study ABI-H2158-201, in accordance with the ABI-H2158-201 Protocol Clarification Letter for Amendment 2 dated 14 Dec 2020, 07 September 2021, subjects were instructed to complete the follow-up assessments through 12 weeks after the last dose of study medication.

Throughout the 12-week follow-up period, all subjects should continue treatment with ETV.

Figure 1-1. Study Overview

Abbreviations: PBO: placebo; ETV: entecavir; HBeAg: hepatitis B “e” antigen.

1.3. Sample Size and Power

It is planned that approximately 80 subjects (40 subjects per Cohort 1 and Cohort 2) will be enrolled in this study. Subjects will be randomized to receive either 300 mg ABI-H2158 or PBO or in a 3:1 ratio. That is, 30 subjects randomized to treatment with ABI-H2158 per Cohort 1 and Cohort 2 and 10 subjects will be randomized to treatment with PBO per Cohort 1 and 2. This sample size is not based on statistical considerations but is considered adequate for a proof-of-concept study.

1.4. Methods of Assigning Subjects to Treatment

1.4.1. Randomization

Within each treatment cohort, randomization of eligible subjects to their respective treatment assignments will be performed centrally using an Interactive Response Technology (IRT) system. Following successful completion of Screening assessments and confirmation of subject eligibility, site personnel will enter the subject specific information in the IRT system and following acceptable completion of the procedure will receive a subject identification number and treatment assignment. Additional information on the use of the IRT is provided in the IRT User Manual.

In Cohort 1, the IRT system will assign treatment-naïve subjects with HBeAg positive cHBV subjects in a 3:1 ratio to receive either 300 mg ABI-H2158+ETV (n=30) versus matching PBO+ETV (n=10). Individual subject treatment assignments will be stratified according to the HBV DNA level measured at the Screening visit (ie, $\geq 8.0 \log_{10}$ IU/mL versus $< 8.0 \log_{10}$ IU/mL).

In Cohort 2, the IRT system will assign treatment-naïve subjects with HBeAg negative cHBV subjects in a 3:1 ratio to receive either 300 mg ABI-H2158+ETV (n=30) versus matching

PBO+ETV (n=10). Individual subject treatment assignments will be stratified according to the HBV DNA level measured at the Screening visit (ie, $\geq 6.0 \log_{10}$ IU/mL versus $< 6.0 \log_{10}$ IU/mL).

